#### **3.1.2 Exclusion Criteria**

- Active history of photosensitivity (e.g. xeroderma pigmentosum, lupus erythematosus, porphyria, severe polymorphous light eruption, solar urticaria)
- Any suspicion that the psoriasis is of the photosensitive variant.
- Any medical condition that could be aggravated or may cause extreme discomfort during the study period.

### **3.2 STUDY PROCEDURES**

#### **3.2.1 Dose Determination:**

The initial dose will be determined by one of the following methods:

- **Sunburn Test/Minimal Erythema Dose (MED) Test:** This test will be performed during the screening visit to determine the initial dose of the Excimer laser. This involves exposing spots on the buttock or lower back to increasing doses of UVB via the Excimer laser. The redness generated from these exposures will be evaluated at Visit 2 by visual evaluation to determine the initial laser dose. The initial dose will be anywhere from 1-4x the MED. Patients who choose this method will have to come back for Visit 2 to determine the dose.
- **Visual MED Test:** If this method is chosen, a study doctor will visually determined the MED during the screening visit based on the patient's skin type and thickness of the psoriasis plaques. Patients who choose this method will not have to come in for Visit 2.

#### **3.2.2 Excimer Laser Irradiation:** This is a standard clinical procedure approved for the treatment of psoriasis. Initial laser dose will be anywhere from 1-4x the MED,

**University Hospitals Case Medical Center**  
**Department of Dermatology**  
**Protocol**

**Protocol Title:** Effects of UVB Excimer Laser on Serum Inflammatory Markers in Patients with Psoriasis

**Principal Investigator:** [name], NP

**Co-Principal Investigator:** [name]

depending on thickness of the plaque. Escalation will be 25-50% increase in dose per treatment if there is no residual erythema, 25% increase per treatment if there is mild residual erythema, and 0% increase per treatment if there is moderate residual erythema. Investigator also has the option to skip a treatment, if there is above moderate erythema, or significant patient discomfort exists. Patients will receive treatment twice a week until one of the following:

- PASI 75 Improvement
- Patient reaches a maximum of 20 treatments

**3.2.3 Optional Punch Biopsy:** Up to 8mm punch biopsies may be taken at the screening visit and final visit from a psoriasis lesion. The tissue samples will be used for histology and undergo standard H&E staining to evaluate the differences before and after Excimer laser treatment. Patients may still participate in this study if they choose to not donate punch biopsies. This procedure involves the removal of a small circle of skin (pencil eraser-sized) using a cookie cutter-like instrument. Lidocaine is used to numb the area to be removed before obtaining the biopsy and then 1-2 stitches are used per biopsy site to prevent bleeding, speed healing and improve the appearance. This procedure may last up to an hour depending on the number of biopsy sites. The stitches are then removed 7-14 days later.

**3.2.4 PASI Scoring:** PASI will be determined for all subject at the Screening Visit, Visit 8, Visit 16, at Visit 23 Final/Termination Visit and, if applicable, the 3 month follow-up visit. The PASI is a measure of psoriatic disease severity taking into account qualitative lesion characteristics (erythema, thickness, and scaling) and degree of skin surface area involvement on defined anatomical regions. The PASI is a validated instrument that has become standard in clinical trials for psoriasis. Psoriasis Area Severity Index scores range from 0 to 72, with higher scores reflecting greater disease severity. Erythema, thickness, and scaling are scored on a scale of 0 (none) to 4 (very severe) on 4 anatomic regions of the body: head, trunk, upper limbs, and lower limbs. Degree of involvement on each of the 4 anatomic regions is scored on a scale of 0 (no involvement) to 6 (90% to 100% involvement). The total qualitative score (sum of erythema, thickness, and scaling scores) is multiplied by the degree of involvement for each anatomic region and then multiplied by a constant. These values for each anatomic region are summed to yield the PASI score.

**3.2.5 Physician Global Assessment (PGA):** PGA skin evaluation will be performed at the Screening visit, Visit 8, Visit 16, Visit 23 Final/Early Termination Visit, and, if applicable, the optional 3 month follow-up visit. This assessment is a scale from 0 (clear) to 5 (severe). It is a global assessment of the subject's psoriasis based on the severity of induration, scaling and erythema.

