#### **3.3.3 Treatment Visits (Visits 3-22) (estimated time: up to 1 hour):**

***\*Patients will undergo Treatment twice a week until they reach a PASI 75 improvement, or until they reach the maximum of 20 total treatments\****

- Study staff will review concomitant medications, any AEs since the previous visit, and procedures with each subject.
- Subjects will have their psoriasis clinically evaluated through PASI scoring and PGA every four weeks during Visit 8 and Visit 16.
- During Visit 8 and Visit 16, treated plaques will be evaluated using a chromameter to measure hyperpigmentation and erythema that may be caused by the laser.
- Subjects will have plaque/body photographs throughout this study.
- Subjects will undergo standard clinical treatment with an Excimer Laser.

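### Section 3.2.2 states no exception for the first dose after a skipped treatment, so its escalation steps, taken literally, allow 1.25-1.5 times the last delivered dose before that dose has been repeated and tolerated

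*Combined protocol and SAP*

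**What the plan says.** Section 3.2.2 ties each step to the redness present at the visit. For a clear site, "Escalation will be 25-50% increase in dose per treatment if there is no residual erythema". For lesser degrees of redness it gives "25% increase per treatment if there is mild residual erythema, and 0% increase per treatment if there is moderate residual erythema". Beyond moderate there is no percentage, only this: "Investigator also has the option to skip a treatment, if there is above moderate erythema, or significant patient discomfort exists".

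The frequency is fixed: "Patients will receive treatment twice a week until one of the following", with PASI 75 or a count of treatments as the stopping points. Section 3.3.3 repeats the limit, "until they reach the maximum of 20 total treatments". The starting dose varies, "depending on thickness of the plaque", so doses may already differ between plaques on one patient.

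No other section supplies a post-skip dose:

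- Section 3.2.1 deals only with the initial dose.
- Section 3.3.3 says of the treatment visits: "Subjects will undergo standard clinical treatment with an Excimer Laser", and before that "Study staff will review concomitant medications, any AEs since the previous visit, and procedures with each subject".
- The schedule in Section 3.4 adds timing but no dose rule.
- Section 4.2 lists redness, scaling and occasional blistering as expected, without a dose response to them.
- Section 15.1 mentions an action plan of the PI for adverse events. Items A-C, which follow, cover responsibility, grading, attribution, follow-up and reporting, and state no dose action.

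**The concern.** The rule looks at redness on the day and carries nothing forward from an earlier over-reaction. A skip gives the redness another 3-4 days to fade. If it fades, the site falls in the clear or mild category, and the only written step for either is upward. A patient who skipped for discomfort without redness is in the same position.

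The dose that provoked the strongest reaction could therefore be exceeded at the next treatment before it has been repeated and tolerated. A moderate reactor, by contrast, gets a repeat of the same dose first. What is at stake is a second avoidable burn or blister at a treated site. The safeguard is the investigator's judgment, not the text.

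**Working it through.** **Inputs.** Steps from Section 3.2.2: none +25% to +50%, mild +25%, moderate 0%. Interval: twice weekly. Assumption: the base for the percentage is the last delivered dose, D; the protocol does not name it. Redness on return may be none, mild or moderate, and the documents give no probabilities for these.

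**Formula.** Next dose = D × (1 + stated increase for the redness seen that day).

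**Step 1, the plan's own steps as multipliers.** None: 1.25 to 1.50. Mild: 1.25. Moderate: 1.00.

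**Step 2, two patients by twice-weekly slot.** Both receive D at slot 1. The over-reactor skips slot 2. The moderate reactor is treated at slot 2 with D × 1.00 = D.

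| Redness at slot 3 | Over-reactor, slot 3 | Moderate reactor, slot 3 |
|---|---|---|
| None | 1.25-1.50 D | 1.25-1.50 D |
| Mild | 1.25 D | 1.25 D |
| Moderate | 1.00 D | 1.00 D |

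For the same redness at slot 3 the two doses are identical. The difference is that the moderate reactor has already had D twice and the over-reactor only once.

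**Step 3, total over slots 1-3.** Over-reactor: D + 0 + (1.0 to 1.5) D = 2.0 to 2.5 D. Moderate reactor: D + D + (1.0 to 1.5) D = 3.0 to 3.5 D. The skip lowers the total, so this is not a cumulative-dose problem.

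**Step 4, effect of capping the first post-skip dose at D.** From 1.25 D to D is a reduction of 1 - 1/1.25 = 20%. From 1.50 D to D it is 1 - 1/1.50 = 33%. So the first post-skip dose falls by at least 20-33% if the site is clear and by at least 20% if redness is mild. It need not change if redness is still moderate. Escalation then resumes at slot 4 at the earliest, one step behind the moderate reactor.

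**The case against.** A reader might infer that the protocol directs a higher dose for the stronger reactor, and so ranks doses the wrong way round. The documents do not support that. Section 3.2.2 is silent on the dose after a skip, and 1.25-1.5 D is what results only if the general steps are applied with no exception. The steps themselves become more cautious as redness increases, and nothing forbids returning at D or lower.

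A reader might also infer that the over-reactor overtakes the moderate reactor. That compares slot 3 for one patient with slot 2 for the other. At the same slot they are due the same dose, and the over-reactor has received less in total.

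The case for leaving the text alone has further weight. The top figure needs redness to fade from above moderate to none, and even then the investigator may choose 25%. The starting dose, the size of the step and the skip are all left to the investigator. Adverse events are reviewed at each treatment visit, so the first reaction would be known before the next dose is set. The PI's action plan is not reproduced, so it may contain a dose rule. Nothing shows that any patient was dosed this way, and no effect on the serum-marker or chromameter analyses is claimed here.

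These points limit how much the gap matters, but they do not close it. For a clear or mildly red site the lowest written step is +25%. An investigator who wants to hold or reduce after a skip must go beyond the wording.

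**Conclusion.** The point holds as a minor safety wording fix. Taken literally, Section 3.2.2 allows the first dose after a skip to be 1.25-1.5 D at a clear site or 1.25 D at a mildly red one, without a tolerated repeat of D. With moderate redness there is no increase.

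This rests on D being the base for the percentages and on the investigator making no adjustment. How often it would arise cannot be estimated, because the documents give neither the rate of above-moderate reactions nor the time for redness to fade.

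**What to change.** **Main change.** Add to Section 3.2.2 that after any skip for above-moderate erythema, blistering or significant discomfort, the first treatment to that site is given at no more than the last delivered dose. The investigator may go lower, and escalation resumes only once that dose has been tolerated. The same sentence would settle the base dose for this situation.

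**Cost.** A per-site dose record, and about one escalation step per event. Twenty treatments contain 19 steps, so one step is 1/19 = 5% of a full course. The share is larger if treatment stops early at PASI 75. PASI is scored at Visits 8 and 16. Counting one treatment per visit from Visit 3, these are treatments 6 and 14, with 5 and 13 steps behind them. One step is then 1/5 = 20% or 1/13 = 8%.

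**Optional and secondary.** Make withholding mandatory at a site with above-moderate erythema or blistering, instead of leaving the skip optional. This goes beyond the post-skip gap and would need a definition of the redness grades, which the protocol does not give. Where an investigator would otherwise have treated, it also costs one slot for that site. That is half a week on a 10-week course (20 treatments / 2 per week) if made up, or 1 of 20 treatments (5%) if not. The documents do not say which applies.

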**University Hospitals Case Medical Center**  
**Department of Dermatology**  
**Protocol**

**Protocol Title:** Effects of UVB Excimer Laser on Serum Inflammatory Markers in Patients with Psoriasis

**Principal Investigator:** [name], NP

**Co-Principal Investigator:** [name]

**3.2.6 Chromameter Assessment:** Treated plaques will be evaluated using a chromameter as an objective measure of hyperpigmentation and erythema at Screening Visit, Visit 8, Visit 16, Visit 23 Final/Early Termination Visit, and, if applicable, the 3 month follow-up visit. The chromameter uses the L\*a\*b\* color system. L\* measures skin reflectance or lightness, a\* measures red to green color saturation, b\* measures yellow to blue color saturation. Hyperpigmentation of treated plaques will be assessed via L\*. L\* values of treated plaques will be compared to L\* values of normal, untreated skin. Erythema of treated plaques will be assessed via a\*. a\* values of treated plaques will be compared to a\* values of normal, untreated skin. These values will also be compared from visit to visit.

**3.2.7 Limited Medical Exam:** Medical and Dermatological history, demographic information, concomitant medications, vital signs, height, weight, and BMI will be collected during Visit 1/Screening Visit.

**3.2.8 Blood Draw:** Blood will be drawn at Visit 1/Screening Visit and at Visit 23 Final/Early Termination Visit by venipuncture and will be evaluated for:

- Serum Inflammatory Markers: (e.g. Levels of CRP, resistin, MPO and S100, etc) as quantified via ELISA kits [ $\sim$ 10mL blood].
- Pro-Inflammatory Monocytes (optional): Populations of monocytes will be characterized in the blood and via flow cytometry analysis [ $\sim$ 60mL blood].

**3.2.9 Questionnaires:** Subjects will be asked to complete two questionnaires.

**3.2.5.1 Patient Satisfaction Survey:** Patients will be asked to complete a survey, scoring their satisfaction with the treatment at Visit 23 Final/Early Termination Visit.

**3.2.5.2 Nutrition Questionnaire:** Patients will be asked to complete a survey about their nutritional habits at Visit 1/Screening Visit.

**3.2.10 Photographs:** Participants will have a photographic record of their skin made throughout this study at the discretion of the study doctor to document any changes in the psoriasis from the treatment. Photographic records provide objective data on skin lesions of persons with skin disease and potential changes that may occur over time in the disease. Photography gives us a tool to compare clinical appearance with laboratory and research findings. Clinical images will be stored as digital images electronically. In the event that a photograph is taken of the patient's head or any other identifiable feature, the patient's identity may become known. Every precaution will be taken to protect the patient's identity, including blacking-out the patient's eyes on any photographs involving the face.

### **3.3 STUDY VISITS**

#### **3.3.1 Visit 1: Screening Visit (estimated time: ~ 90 minutes)**

- Subjects will review the Institutional Review Board (IRB) approved Informed Consent Form (ICF) with the study staff. After all study procedures have been discussed and all questions have been answered, subjects will affirm participation by signing and dating the consent form.
- Inclusion/exclusion criteria will be reviewed and subject eligibility confirmed.
- Study staff will review concomitant medications and procedures with each subject.
- Medical and Dermatological History information will be collected.
- Vital signs, height, weight and BMI will be collected and recorded.
- Subjects will have their psoriasis clinically evaluated through PASI scoring and PGA.
- A chromameter will be used to evaluate pigmentation before treatment.
- Subjects will have plaque/body photographs taken
- Subjects will undergo a Sunburn MED Test or Visual MED Test.
- Subjects will complete a dietary/nutrition questionnaire.
- Subjects will undergo a pre-treatment blood draw.
- An optional, pre-treatment punch biopsy may be taken from a psoriasis lesion.

#### **3.3.2 Visit 2 (estimated time: up to 15 minutes)**

*\*\*This visit will only be scheduled for patients undergoing the Sunburn MED Test\*\**

- Study staff will review concomitant medications, any AEs since the previous visit, and procedures with each subject.
- Study staff will determine the MED through visual evaluation.
- Patient may begin first treatment/Visit 3 during this visit.

#### **3.3.3 Treatment Visits (Visits 3-22) (estimated time: up to 1 hour):**

***\*Patients will undergo Treatment twice a week until they reach a PASI 75 improvement, or until they reach the maximum of 20 total treatments\****

- Study staff will review concomitant medications, any AEs since the previous visit, and procedures with each subject.
- Subjects will have their psoriasis clinically evaluated through PASI scoring and PGA every four weeks during Visit 8 and Visit 16.
- During Visit 8 and Visit 16, treated plaques will be evaluated using a chromameter to measure hyperpigmentation and erythema that may be caused by the laser.
- Subjects will have plaque/body photographs throughout this study.
- Subjects will undergo standard clinical treatment with an Excimer Laser.

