**University Hospitals Case Medical Center**  
**Department of Dermatology**  
**Protocol**

**Protocol Title:** Effects of UVB Excimer Laser on Serum Inflammatory Markers in Patients with Psoriasis

**Principal Investigator:** [name], NP

**Co-Principal Investigator:** [name]

**3.3.4 Visit 23: Final Visit/Early Termination Visit [2 days-2 weeks after last treatment]  
(estimated time: up to 1 hour )**

- Subjects will have their psoriasis clinically evaluated through PASI scoring and PGA.
- Treated plaques will be evaluated using a chromameter to measure hyperpigmentation and erythema that may be caused by the laser.
- Subjects may have plaque/body photographs taken.
- Subjects will undergo a post-treatment blood draw.
- Optional, post-treatment punch biopsies may be taken from a psoriasis lesion.
- Subjects will fill out the Patient Satisfaction Survey.

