**3.4 Schedule of Events**

	Visit 1: Screening	Visit 2 (Only if Sunburn/MED was done)	All Treatment Visits (Visits 3-22)	Treatment Visit 8 and Visit 16	Visit 23: Final Visit/Early Termination Visit	**Optional 3 Month Follow- Up Visit
Informed Consent	X					
Limited Medical Exam	X					
PASI & PGA	X			X	X	X
Photographs*	X	X	X	X	X	X
Chromameter	X			X	X	X
Blood Draw	X				X	
Concomitant Med Assessment	X	X	X	X	X	X
Optional Sunburn/MED Test	X					
Optional Sunburn/MED assessment		X				
Excimer Laser Treatment			X	X		
Nutrition Questionnaire	X					
Patient Satisfaction Questionnaire					X	
Adverse Event Assessment	X	X	X	X	X	X
Optional Sub-Study: Additional Blood	X				X	
Optional Sub-Study: Punch Biopsy	X				X	

*\*Photographs will be taken throughout this study at the discretion of the study doctor to document any changes in the psoriasis from the laser treatment.*

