## **14. DATA ANALYSIS PLAN**

- 14.1 Clinical Outcome:** Clinical evaluation through PASI scoring and PGA will be performed, supported by photographic documentation. Percent change in PASI and number of treatments to obtain PASI 75 improvement will be calculated for each patient and results summarized as descriptive statistics using means and standard deviations.
- 14.2 Serum inflammatory markers:** Levels of inflammatory markers in the serum e.g. CRP, resistin, MPO and S100. will be quantified pre and post treatment via ELISA kits and correlated with PASI score, total number of treatments received, BMI and nutrition data, using multivariate regression analyses.
- 14.3 Optional flow cytometry analysis:** Populations of monocytes will be characterized in the blood and response to excimer laser expressed in improvement in PASI scores will be correlated with levels of specific pro-inflammatory monocytes using Pearson correlation coefficient. Level of pro-inflammatory monocytes will also be correlated with levels of CRP, resistin, MPO, S100.
- 14.4 Chromameter Assessment:** Hyperpigmentation of treated plaques will be assessed via  $L^*$ .  $L^*$  values of treated plaques will be compared to  $L^*$  values of normal, untreated skin. Erythema of treated plaques will be assessed via  $a^*$ .  $a^*$  values of treated plaques will be compared to  $a^*$  values of normal, untreated skin. These values will also be compared from visit to visit. They will also be correlated with response to treatment.
- 14.5 Patient Satisfaction Questionnaire:** Each item in the survey will be scored from 1-5. Scores will be summarized and descriptive statistics will be used. Satisfaction scores will also be correlated with PASI improvement.

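### Treatment stops at PASI 75, but on-treatment PASI is scheduled only at Visits 8 and 16, so a responder can receive up to 7 further treatments (8 if that day's dose is given) and the treatment count to PASI 75 is known only within three intervals

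*Combined protocol and SAP*

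**What the plan says.** **Stop rule.** Section 3.2.2 states: "Patients will receive treatment twice a week until one of the following", and then lists PASI 75 and a maximum of 20 treatments. Section 3.3.3 repeats the rule: "Patients will undergo Treatment twice a week until they reach a PASI 75 improvement, or until they reach the maximum of 20 total treatments". Section 3.2.2 also allows for missed doses: "Investigator also has the option to skip a treatment, if there is above moderate erythema".

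**PASI schedule.** Section 3.2.4 reads "PASI will be determined for all subject at the Screening Visit, Visit 8, Visit 16, at Visit 23", with an optional 3-month visit to follow. Section 3.3.3 has patients "clinically evaluated through PASI scoring and PGA every four weeks during Visit 8 and Visit 16". In section 3.4, PASI is marked in the column headed "Treatment Visit 8 and Visit 16" but not in the column for all treatment visits. Laser treatment is marked in both. After Visit 16 the next scheduled PASI is at Visit 23, which section 3.3.4 places between 2 days and 2 weeks after the last treatment.

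**Analysis.** Section 14.1 plans percent change in PASI and a count of treatments up to the response: "PASI 75 improvement will be calculated for each patient and results summarized as descriptive statistics using means and standard deviations".

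The protocol does not say whether PASI is scored before or after that day's dose, whether the dose is withheld once PASI 75 is met, or how patients who never reach PASI 75 enter the summary.

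**The concern.** The stop rule needs a PASI score, and 18 of the 20 treatment visits (20 - 2) have none scheduled. Two things follow.

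- **Exposure.** A patient who reaches PASI 75 between checks continues to receive UV after meeting the protocol's own stop criterion.
- **Outcome.** The number of treatments at which PASI 75 was reached is not observed. Only the count at the first assessment showing it is. If that count is entered as the patient's value, the mean tends to be too high when PASI improves steadily. Patients who never reach PASI 75 have no count, so a mean over the available values describes responders only, although 14.1 promises a value for each patient.

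**Working it through.** **Inputs.** Treatment visits are Visits 3 to 22, and Visit 3 is the first treatment (3.3.2, 3.3.3). Treatment is twice weekly with a cap of 20 (3.2.2, 3.3.3). On-treatment PASI is at Visits 8 and 16 (3.2.4, 3.3.3, 3.4). The counts below assume no skipped dose and no early withdrawal.

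**The plan's own figure.** 22 - 3 + 1 = 20 treatments, which matches the stated maximum.

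**Which treatments are the checks?** Treatment number = visit number - 2.

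- Visit numbering: Visit 8 is treatment 6, at (6 - 1)/2 = 2.5 weeks after the first treatment. Visit 16 is treatment 14, at (14 - 1)/2 = 6.5 weeks.
- Four-week reading: at two treatments a week, four weeks is 8 treatments. The 8th and 16th treatments fall at 3.5 and 7.5 weeks. The column heading in 3.4 can also be read this way.

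The gap between the two checks is 8 treatments (four weeks) on both readings, so only the starting point is in doubt.

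**Excess treatments.** If PASI 75 is first truly reached after treatment k, the excess is the number of treatments given when it is detected, minus k.

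| Reading | Scoring rule | Intervals for k | Treatments given at detection | Maximum excess per interval |
|---|---|---|---|---|
| Treatments 6, 14 | before dose, dose withheld | 1-5, 6-13, 14-20 | 5, 13, 20 | 4, 7, 6 |
| Treatments 6, 14 | before dose, dose still given | 1-5, 6-13, 14-20 | 6, 14, 20 | 5, 8, 6 |
| Treatments 6, 14 | after dose | 1-6, 7-14, 15-20 | 6, 14, 20 | 5, 7, 5 |
| Treatments 8, 16 | before dose, dose withheld | 1-7, 8-15, 16-20 | 7, 15, 20 | 6, 7, 4 |
| Treatments 8, 16 | before dose, dose still given | 1-7, 8-15, 16-20 | 8, 16, 20 | 7, 8, 4 |

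The worst case by visit number is PASI 75 reached just after treatment 6: treatments 7 to 13 make 7 extra, and treatment 14 makes 8. On the other reading it is just after treatment 8: treatments 9 to 15 make 7, and treatment 16 makes 8.

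**Effect on the mean.** The documents give no distribution of response times. As an illustration, take k spread evenly over 1 to 20, with scoring before the dose and the dose withheld.

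- True mean: (1 + 20)/2 = 10.5.
- Recorded mean, treatments 6 and 14: (5×5 + 8×13 + 7×20)/20 = 269/20 = 13.45.
- Recorded mean, treatments 8 and 16: (7×7 + 8×15 + 5×20)/20 = 269/20 = 13.45.
- Mean excess on either reading: 13.45 - 10.5 = 2.95.

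**Effect of two added checks, scored before dosing.**

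- Visit numbering, adding Visits 12 and 20 (9 and 17 treatments completed): detection at 5, 9, 13, 17 or 20. Maximum excess per interval is 4, 3, 3, 3, 2. The even-spread mean is (10 + 6 + 6 + 6 + 3)/20 = 1.55.
- If the 8th and 16th treatments are meant, adding the 4th and 12th (3 and 11 completed): detection at 3, 7, 11, 15 or 20. Maximum excess per interval is 2, 3, 3, 3, 4. The even-spread mean is (3 + 6 + 6 + 6 + 10)/20 = 1.55.

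**The case against.** The strongest reply is that the text says to treat until PASI 75, does not forbid extra scoring, and has staff seeing the patient at every treatment visit, where residual erythema guides the dose and photographs may be taken. Applying a response rule only at scheduled assessments is also ordinary practice. Part of this stands: the investigator is not blind between checks, and 7 or 8 is a worst case, not an expectation. But PASI 75 needs a full four-region score, nothing in the protocol triggers one between checks, and scoring at discretion would make detection differ between patients.

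It is also fair to say that the reach is small. The study's aims are serum markers, hyperpigmentation and erythema. This is one descriptive summary in 24-27 patients with no test attached. The laser is an approved treatment, adjusted for erythema and capped at 20.

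Four stronger readings are tempting, and the documents do not support them:

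- *The plan contains an arithmetic error.* It does not. Visits 3-22 give exactly 20 treatments. The fault lies in the assessment schedule and the definition of the outcome.
- *The SD is distorted in a known direction.* That depends on when responses occur, which the documents do not say.
- *The marker regressions are compromised.* Section 14.2 uses total treatments received, which remains exactly countable.
- *Responders will be harmed by the extra doses.* Nothing in the documents quantifies such harm.

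**Conclusion.** The concern holds as a mismatch between a stop rule and the schedule that should feed it. On either reading of the check times, and with no skips, up to 7 treatments can follow PASI 75 before it is scheduled to be detected, or 8 if that day's dose is still given. The treatment count in 14.1 is known only within three intervals. Its mean tends to run high if counts at detection are used: by 2.95 treatments under the assumed even spread with scoring before the dose and the dose withheld. A chance low score could pull the other way. Skipped doses change the number of treatments completed at each check but add no scheduled check. Non-responders have no value and no stated handling. The plan should be changed on this point, but the consequence is confined to a descriptive outcome and to a bounded number of extra treatments.

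**What to change.** 1. **Sections 3.2.2, 3.3.3 and 3.4.** State the treatment numbers at which PASI is scored, so that the visit labels and the four-week wording agree. Score before dosing, apply the stop rule there, and give no dose once PASI 75 is met. Alone, this only brings the maximum excess from 8 to 7.
2. **Section 14.1.** Replace the mean and SD of the treatment count with the number and percentage of all enrolled patients first meeting PASI 75 at each scheduled assessment, the treatments completed by then, and the number who never met it. Formal interval-censored modelling is not needed.
3. **Sections 3.2.4, 3.3.3 and 3.4.** To reduce treatment past the stop criterion, add two PASI scorings before dosing: Visits 12 and 20 under visit numbering, or the 4th and 12th treatments if the 8th and 16th are the intended checks. With no skips, either choice cuts the maximum excess from 7 to 4.

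**Cost.** Items 1 and 2 are a few sentences; the loss is a single mean. Item 3 adds at most 2 short scorings per patient at visits already held, 2×24 = 48 to 2×27 = 54 in total, and slightly raises the chance of stopping on one low score. Scoring at all 18 other treatment visits would add up to 18×24 = 432 to 18×27 = 486, which is out of proportion for a descriptive outcome.
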